7.2.1 Hydroxychloroquine

Patients randomized to an HCQ-containing arm will receive HCQ at a dose of 600 mg orally twice daily. Capsules of HCQ are available in 200 mg strength, thus patients will initially start with 3 capsules twice daily for a total of 6 capsules per day. HCQ will be administered in divided doses (BID). When taking HCQ twice daily, the two daily doses should be taken 12 hours apart as close to 9am and 9pm as possible and documented clearly on the patient calendar. Patients receiving antacids, sucralfate, cholestyramine, and/or bicarbonate should have the HCQ drug dose administered at least 1 hour before or 2 hours after these medications. Hydroxychloroquine will be obtained through a written prescription by study MD as an initial 28- day supply and refilled every cycle. Patients will be required to bring the prescription to their visit on day 1 of each cycle, along with previous months’ pill container so that pill counts can be performed. In addition, treatment diaries will be used to monitor adherence to therapy. Patients are required to bring the pill bottles and treatment diaries to each visit. Missed or vomited doses should not be made up; patient should resume planned dose at next dosing interval.

7.2.2 Everolimus

Patients randomized to an EVE-containing arm will receive EVE as a dose of 10 mg orally daily, on a continuous basis. Patients will be instructed to take EVE in the morning, at the same time each day. EVE may be taken with or without food. If vomiting occurs, no attempt should be made to replace the vomited dose. All dosages prescribed and dispensed to the patient and all dose changes during the study must be recorded. EVE will be provided by Novartis Pharmaceuticals Corporation. Antiemetic prophylaxis is not required. However, control of nausea and vomiting may require institution of multiple anti-emetic medication including phenothiazines or 5-HT3 antagonists. Due to its interaction with P450 enzymes, aprepitant use should be avoided.

7.3 Adjuvant Endocrine Therapy

Patients with hormone receptor positive primary or residual tumor will continue on their assigned adjuvant endocrine therapy throughout the duration of the trial. Note that tamoxifen is not allowed during the study due to drug-drug interactions with HCQ (see Section 7.6 and Table 3).

7.4 Concomitant Treatment and Supportive Care Guidelines

Necessary supportive measures for optimal medical care will be provided during the study (including administration of prophylactic antiemetic medication if

considered appropriate by the Investigator).

7.4.1 Antiepileptics:

Because HCQ has known effects on P450 enzymes, patients requiring anti-convulsants may be treated with any of the non-enzyme inducing anti-convulsants which include: felbamate, valproic acid, gabapentin, lamotrigine, tiagabine, topiramate, zonisamide, or levetiracetam.

7.4.2 Hematologic Growth Factors

The use of hematologic growth factors (filgrastim, pegfilgrastim, epoetin alfa) is permitted to provide optimal care for patients with severe myelosuppression.

7.4.3 Bone targeting therapies

Bone targeting therapies such as bisphosphonates and RANK ligand inhibitors may be administered per standard of care guidelines. Zometa or denosumab may be given if clinically indicated.

7.5 Concomitant Medications

The case report form must capture the concurrent use of all other drugs, over-the-counter medications, or alternative therapies. Patients must adhere to the following:

- Patients will be instructed not to take any additional medications (including over-the-counter products) during the course of the study without prior consultation with the investigator. At each visit, the investigator will ask the patient about any new medications he/she is or has taken after the start of the study drug.
- All Concomitant medications/Significant non-drug therapies taken within 28 days of starting study treatment through the 30- day safety follow up visit, including physical therapy and blood transfusions, should be recorded.
- Patients on chronic medications that can be given concomitantly with the study agents should be continued. The investigator should instruct the patient to notify the study site about any new medications he/she takes after the start of the study drug. All medications (other than study drug) and significant non-drug therapies (including physical therapy and blood transfusions) administered after the patient starts treatment with study drug, and any changes in dosing should be recorded.
- All supportive measures consistent with optimal patient care can be given throughout the study at the discretion of the treating physician, as long as they are not part of the list of prohibited medications. In general, the use of any concomitant medication/therapies deemed necessary for the care of the patient is permitted with the following considerations:
- Prophylactic anti-emetics should be started only once the patient experienced nausea or vomiting at the discretion of the investigator. It is recommended that patients use drugs that do not cause QT prolongation.
- Patients may not receive radiotherapy while on this trial.
- Other investigational therapies must not be used while the patient is on the study

- Anticancer systemic therapy other than the study treatments must not be given to patients while on the study. If such agents are required for a patient then the patient must be discontinued from the study.
- Herbal preparations are not allowed throughout the study. These herbal preparations include, but are not limited to: St. John’s wort, Kava, ephedra (ma huang), ginkgo biloba, dehydroepiandrosterone (DHEA), yohimbe, saw palmetto, and ginseng. Patients should stop using these herbal preparations 14 days prior to first dose of study drug

7.6 Drug-Drug Interactions

The following restrictions apply during the entire duration of the study:

- No other investigational therapy should be given to patients.
- No anticancer agents other than the study medication should be given to patients. If such agents are required for a patient then the patient must first be withdrawn from the study.
- Hydroxychloroquine interacts with CYP enzymes, causing potential drug-drug Interations. CYP3A4 modifiers are described below (Table 3) and must be evaluated carefully. Examples are shown in the table. A comprehensive list of cytochrome P450 isoenzymes and CYP3A4 inhibitors, inducers, and substrates can be found at <http://medicine.iupui.edu/flockhart>. This website is continually revised and should be checked frequently for updates.
- Co-administration with strong inhibitors of CYP3A4 (e.g., ketoconazole, itraconazole, ritonavir) or P-glycoprotein (PgP) should be avoided. Seville orange, star fruit, grapefruit and their juices affect P450 and PgP activity. Concomitant use should be avoided
- Co-administration with moderate CYP3A4 inhibitors (e.g., erythromycin, fluconazole) or PgP inhibitors should be used with caution. If patient requires co-administration of moderate CYP3A4 inhibitors or PgP inhibitors, reduce the dose of EVE to 5 mg daily. Additional dose reductions to 5 mg every other day may be required to manage toxicities. If the inhibitor is discontinued the EVE dose should be returned to the dose used prior to initiation of the moderate CYP3A4/PgP inhibitor.
- No chronic treatment with systemic steroids or other immunosuppressive agents (at a dose equivalent of greater than 20 mg prednisone per day) or other immunosuppressive agents) is allowed. Topical or inhaled corticosteroids are allowed.
- For hydroxychloroquine, there are known drug interactions with the following medications: penicillamine, telbivudine, botulinum toxins, digoxin, metoprolol, aurothioglucose, and propafenone. Depending on the specific drug, HCQ increases the levels of these other drugs, or interferes with the activity of the agent (specifically with botulinum toxin) and the combination should be used with caution.

Table 3: Partial List of Prohibited Medications Based on CYP Metabolism

Substrates (competitive inhibition)	
Antibiotics ¹ : clarithromycin* erythromycin	Calcium Channel Blockers: amlodipine diltiazem

telithromycin* Anti-arrhythmics: quinidine Benzodiazepines: alprazolam diazepam midazolam triazolam Immune Modulators: cyclosporine tacrolimus (FK506) HIV Protease Inhibitors: indinavir* ritonavir* saquinavir* Prokinetic: cisapride Antihistamines: astemizole chlorpheniramine ⁴⁵	felodipine nifedipine nisoldipine nitrendipine verapamil HMG CoA Reductase Inhibitors ² : atorvastatin cerivastatin lovastatin simvastatin Miscellaneous: aprepitant buspirone haloperidol methadone pimozide quinine sildenafil tamoxifen trazodone vincristine
Inducers	
Carbamazepine Phenobarbital Phenytoin* Rifabutin*	Rifampin* St John's wort Troglitazone
Inhibitors	
Amiodarone Cimetidine Clarithromycin Delaviridine Diltiazem Erythromycin Fluvoxamine* Grapefruit juice Sevilla orange	Indinavir Itraconazole* Ketoconazole* Voriconazole* Posaconazole* Mibefradil Nefazodone* Nelfinavir* Troleandomycin Verapamil

Based on: Ingelman-Sundberg M, Human drug metabolising cytochrome P450 enzymes: properties and polymorphisms, Naunyn Schmiedebergs Arch Pharmacol. 2004 Jan;369(1):89-104. and [<http://www.medicine.iupui.edu/flockhart/clinlist.htm> as of July 13, 2006]

* asterisk denotes strong inhibition/ induction

Please note:

strong inhibitor implies that it can cause ≥ 5 -fold increase in AUC or $\geq 80\%$ decrease in clearance of sensitive CYP substrates

moderate inhibitor implies that it can cause 2 to 5-fold increase in AUC values or 50-80% decrease in clearance of sensitive CYP substrates.

(Distinction is not always categorical as interaction can vary according to conditions).

Macrolide antibiotics: Azithromycin is not a CYP3A substrate. It may therefore be employed where antibiotherapy with a macrolide is desirable in a patient being treated with EVE

Statins: Atorvastatin and pravastatin may be associated with EVE, since a PK interaction study has shown that there is no relevant PK interaction.

7.7 Criteria for Removal from Study

Patients may be removed from the study before completing the full follow-up

period in the event of unacceptable toxicity, or either physician or patient preference.

7.8 Discontinuation of Treatment

Patients who discontinue study treatment prior the final planned dose will enter the follow up phase, and complete all procedures and follow-up dictated by the protocol. Patients who choose to discontinue all study participation, including follow-up, may do so at any time without penalty, by following the procedures outlined in section 7.11. At the time of any treatment discontinuation or withdrawal, site research staff should document the reasons and conditions under which discontinuation of treatment occurred and whether the patient is willing to continue follow up or will be requesting full withdrawal from the study. Each subject has the right to discontinue study treatment or withdraw from the overall study at any time without prejudice. The investigator may discontinue any subject's participation for any reason, including adverse event or failure to comply with the protocol. Because this is a randomized pilot trial following intent-to-treat principals, patients who discontinue study treatment will be followed for study outcomes as outlined in the protocol. Reasons for withdrawal from study treatment include the following:

- Delay in treatment > 28 days due to treatment-related toxicity or major event (if due to treatment-related toxicity, patient will be taken off the treatment that is most likely to be related to the toxicity).
- Disease Recurrence: Remove patient from protocol therapy at the time progressive disease is documented.
- Extraordinary Medical Circumstances: If at any time the treating physician feels constraints of this protocol are detrimental to the patient's health remove the patient from protocol therapy.
- Patient's refusal to continue treatment: In this event, document the reason(s) for withdrawal.
- Failure to comply with protocol (as judged by the investigator such as compliance below 80%, failure to maintain appointments, etc.).

7.9 Withdrawal from Study

Patients who choose to withdraw from study participation (including any additional treatment, follow-up, or study procedures) may do so, without penalty, by sending a request to be withdrawn from the study, in writing, to the Principal Investigator. In addition, this request should specifically address whether research samples that remain in the possession of the study staff can be used for future research per the previously signed consent form. Should the patient request withdrawal from the study, the PI and project manager should be alerted immediately, and updated with the conditions of the request.

7.10 Contraceptive Measures and Reproductive Risks

Female Participants

Female participants should not become pregnant while on this study and for 8 weeks after their last dose of study treatment because the study drugs could have a negative effect on an unborn baby. In addition, female participant should not breastfeed while on this study during treatment and for 2 weeks after the last dose

as these drugs may also affect a breast-feeding child. Pregnant women and women who are breast-feeding are not allowed to participate in this study. If a participant becomes pregnant, the participant will no longer be able to participate in this study.

If a participant is of child bearing potential, she must agree to use two medically accepted forms of birth control including condoms, diaphragms, cervical cap, an intra-uterine device (IUD), surgical sterility (tubal ligation or a partner that has undergone a vasectomy), or oral contraceptives, OR she must agree to completely abstain from intercourse during participation in this study and for 8 weeks after her last dose of study treatment. Abstinence at certain times of the cycle only, such as during the days of ovulation, after ovulation and withdrawal are not acceptable methods of birth control. The participant's form of birth control must be approved by the study doctor.

Even when approved contraceptive methods are used, there is always a small risk that a participant could still become pregnant. If a participant becomes pregnant during the course of this study or up to 8 weeks after the last dose of study treatment, the participant must discontinue study treatment, tell the investigator immediately, and consult an obstetrician or maternal-fetal specialist. If a participant becomes pregnant while on this study, the study staff will ask permission to collect information about the participant's pregnancy.

Male Participants

Male participants should not father a child while on this study and for 8 weeks after the last dose of study treatment, because the drug involved could have a negative effect on an unborn baby. If a participant's spouse or partner has the potential to become pregnant, both the participant and partner must use two medically accepted forms of birth control including condoms, diaphragms, cervical cap, an intra-uterine device (IUD), surgical sterility (vasectomy or a partner that has undergone a tubal ligation), or oral contraceptives, OR the participant must agree to completely abstain from intercourse during participation in this study and for 8 weeks after the last dose of study treatment. Abstinence at certain times of the cycle only, such as during the days of ovulation, after ovulation and withdrawal are not acceptable methods of birth control. The participant's form of birth control must be approved by the study doctor.

Male participants should also inform their partner of the potential harm to an unborn child. If a participant's partner should become pregnant during the course of this study or up to 8 weeks after the participant's last dose of study treatment, the pregnancy will need to be reported to the study doctor immediately, and the participant's partner should promptly notify her doctor. The study doctor will also ask to follow-up on the pregnancy.

Fertility

The potential for everolimus to cause infertility in male and female patients is unknown. However, menstrual irregularities, secondary amenorrhea and associated luteinizing hormone (LH)/follicle stimulating hormone (FSH) imbalance has been

observed in female patients receiving everolimus. Blood levels of FSH and LH increased, blood levels of testosterone decreased, and azoospermia have been observed in male patients receiving everolimus.

8 EXPECTED TOXICITIES AND DOSING DELAYS/DOSE MODIFICATIONS

8.1 Toxicity Criteria

This study will utilize the CTCAE version 4.0 for toxicity and Adverse Event Reporting. A copy of the CTCAE version 4.0 can be downloaded from the CTEP home page (<http://ctep.cancer.gov>). All appropriate treatment areas should have access to a copy of the CTCAE version 4.0

8.2 Anticipated Toxicities of Hydroxychloroquine

Toxicities that can be seen with hydroxychloroquine include:

- Central nervous system: Irritability, nervousness, emotional changes, nightmares, psychosis, headache, dizziness, vertigo, seizure, ataxia, lassitude.
- Dermatologic: Bleaching of hair, alopecia, pigmentation changes (skin and mucosal; black-blue color), rash (urticarial, morbilliform, lichenoid, maculopapular, purpuric, erythema annulare centrifugum, Stevens-Johnson syndrome, acute generalized exanthematous pustulosis, and exfoliative dermatitis).
- Gastrointestinal: Anorexia, nausea, vomiting, diarrhea, abdominal cramping.
- Hematologic: Aplastic anemia, agranulocytosis, leukopenia, thrombocytopenia, hemolysis (in patients with glucose-6-phosphate deficiency).
- Hepatic: Abnormal liver function/hepatic failure (isolated cases).
- Neuromuscular & skeletal: Myopathy leading to progressive weakness and atrophy of proximal muscle groups (may be associated with mild sensory changes, loss of deep tendon reflexes, and abnormal nerve conduction).
- Ocular: Disturbance in accommodation, keratopathy, corneal changes/deposits (visual disturbances, blurred vision, photophobia - reversible on discontinuation), macular edema, atrophy, abnormal pigmentation, retinopathy (early changes reversible - may progress despite discontinuation if advanced), optic disc pallor/atrophy, attenuation of retinal arterioles, pigmentary retinopathy, scotoma, decreased visual acuity, nystagmus.

8.3 Anticipated Toxicities of Everolimus

Toxicities that can be seen with Everolimus include:

- Cardiovascular: Edema, peripheral edema, chest pain, congestive cardiac failure
- Central nervous system: Pain, fever, headache, insomnia, dysgeusia, ageusia
- Dermatologic: Rash, pruritus, nail disorder/thinning, dry skin, acne, erythema, hand-foot syndrome, angioedema
- Endocrine & metabolic: decreased appetite, Hyperglycemia, hypercholesterolemia, hypertriglyceridemia, hyperlipidemia, hypophosphatemia, hypokalemia, diabetes mellitus, dehydration
- Gastrointestinal: Mucositis, nausea, anorexia, diarrhea, abdominal pain, constipation, stomatitis, taste disturbance, vomiting, weight loss, dry mouth, dyspepsia, dysphagia
- Genitourinary: Urinary tract infection
- Hematologic: Anemia, lymphopenia, thrombocytopenia (DLT), leukopenia, neutropenia, pancytopenia, pure red cell aplasia
- Vascular disorders: hemorrhage, hypertension, deep vein thrombosis
- Hepatic: Alkaline phosphatase increased, AST increased
- Neuromuscular & skeletal: Weakness, back pain, arthralgia
- Renal: Creatinine increased, proteinuria, renal failure
- Respiratory: Dyspnea, cough, epistaxis, pharyngitis, pneumonitis, hemoptysis, pulmonary embolism, acute respiratory distress syndrome
- Miscellaneous: Infection (includes abscess, bronchitis, cellulitis, herpes simplex, herpes zoster), hypersensitivity, amenorrhea, aspartate aminotransferase increased alanine aminotransferase increased
- Other Medical Problems: The presence of other medical problems may affect the use of this medicine. For example bowel problems, diabetes, hyperlipidemia (increased blood cholesterol or fats), infection, kidney disease, lung disease (This medicine may worsen these conditions, or brain tumor (Use with caution). This medicine may increase the risk of having serious bleeding in the head.

8.4 Monitoring of EVE suspected toxicities

Patients whose treatment is interrupted or permanently discontinued due to

an adverse event or abnormal laboratory value suspected to be related to EVE must be followed at least weekly until the adverse event or abnormal laboratory resolves or returns to grade ≤ 1 . If a patient requires a dose delay of > 28 days from the intended day of the next scheduled dose, then the patient must be discontinued from the study or continued on HCQ alone if there is evidence of clinical benefit and toxicities resolve to $<$ grade 2.

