8.8.2 Everolimus (EVE) Dose Reduction Guidelines

Known EVE hematological toxicities will not be attributed to HCQ but will only be attributed to EVE and will result in the following EVE dose modifications, as shown in Table 11. Hematologic toxicity of unexpected severity may be attributed to HCQ (in addition to EVE at investigator discretion). Non-hematological toxicities having an attribution to EVE of possible, probable or definite will result in the following EVE dose modifications, as shown in Table 11. For EVE dosing, the patient must have an ANC $\geq 1.0 \times 10^9/L$ and platelet count $> 75 \times 10^9/L$. All non-hematological toxicity grade ≥ 3 (except for alopecia, nausea and vomiting) must have resolved to CTCAE grade ≤ 1 . If toxicity persists, treatment should be delayed by one week for up to 4 consecutive weeks. If after 4 weeks (28 days) of delay all toxicity has still not resolved, any further treatment with EVE should be stopped. HCQ may be continued after EVE has been stopped on the combination arm.

Table 10: EVE Dose Reduction Guidelines

Dose Level	Dose	Reduce to
1	10 mg daily	5 mg daily
-1	5 mg daily	5 mg every other day
-2	5 mg every other day	Discontinue EVE

If any non-hematological toxicity observed Grade ≥ 3 (except for alopecia, nausea and vomiting) and/or if platelets $< 75 \times 10^9/L$ and/or ANC $< 1 \times 10^9/L$, causing delay of two weeks of EVE then the dose should be reduced by one dose level (see Table 10). For patients who would require dose >2 dose reductions EVE will be stopped. If any non-hematological toxicity observed was CTCAE **Grade 4** (except for alopecia, nausea and vomiting) then EVE should be **stopped**.

Table 11: Criteria for dose-modification for suspected EVE toxicity and re-initiation of EVE treatment

Toxicity	Actions
Non-hematological toxicity	
Grade 2 (except pneumonitis – refer to Table 6)	If the toxicity is tolerable to the patient, maintain the same dose. If the toxicity is intolerable to patient, interrupt EVE until recovery to grade ≤ 1 . If resolution occurs ≤ 7 days reintroduce EVE at same dose. If resolution takes > 7 days or if the event returns to grade 2, then interrupt EVE until recovery to grade ≤ 1 . Then reintroduce EVE at lower dose level.

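### For unresolved everolimus toxicity, Section 8.4 and Table 4 take the patient out of the study, while Sections 7.8, 8.8.2 and Table 11 stop only the drug; Table 11 also sends pneumonitis to the hepatitis table

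*Protocol*

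**What the plan says.** **Rules that remove the patient from the study.**

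- Section 8.4, everolimus delay over 28 days: "then the patient must be discontinued from the study or continued on HCQ alone if there is evidence of clinical benefit" and toxicity has resolved to below grade 2.
- Section 8.6.6, Table 4: grade 2 pneumonitis not back to grade 1 or less in 3 weeks, and grade 3 not back in 2 weeks, both lead to withdrawal from the study. Grade 4 leads only to discontinuation of treatment.

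**Rules that stop treatment or one drug.**

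- Section 7.8 lists, among the reasons for withdrawal from study treatment, "Delay in treatment > 28 days due to treatment-related toxicity or major event". If the cause is treatment-related, the "patient will be taken off the treatment that is most likely to be related to the toxicity". Citing intent-to-treat, it adds that "patients who discontinue study treatment will be followed for study outcomes as outlined in the protocol".
- Section 8.8.2: "If after 4 weeks (28 days) of delay all toxicity has still not resolved, any further treatment with EVE should be stopped". HCQ may then continue on the combination arm, with no benefit or grade condition attached.
- Table 11, last row: any toxicity needing more than 28 days of interruption means everolimus is discontinued.

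**Cross-reference.** The grade 2 and grade 3 non-hematological rows of Table 11 both refer pneumonitis to Table 6. Table 6 covers hepatitis B reactivation. The pneumonitis rules are in Table 4.

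**The concern.** One event, an everolimus delay that outlasts 28 days, has two mandatory outcomes depending on which section the site opens. In one, the patient leaves the study. In the other, the patient leaves a drug and stays in follow-up. Section 7.8 treats these as different things: "Each subject has the right to discontinue study treatment or withdraw from the overall study at any time without prejudice".

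What is at stake is the post-treatment data. Patients removed under 8.4 or Table 4 would be selected by everolimus toxicity, so the missing recurrence data would not be a random subset. Section 12.2.2 estimates 3-year RFS to inform a later definitive trial and does not name an estimator. If removed patients were censored at removal, the estimate would rest on their recurrence risk being unrelated to the toxicity that removed them.

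The wrong table number is a separate defect. It matters because it sits in the table that clinicians use to modify dose, and Section 8.5.3 reports fatal outcomes linked to pneumonitis.

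**Working it through.** The point is textual, and the plan gives no figure to reproduce.

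**1. Same trigger, different action.**

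| Place | Trigger | Action | Outcome follow-up |
|---|---|---|---|
| 8.4 | everolimus delay > 28 days | out of the study, or HCQ alone if clinical benefit and toxicity below grade 2 | not stated |
| Table 4, grades 2 and 3 | pneumonitis unresolved at 3 or 2 weeks | out of the study | not stated |
| 7.8 | delay > 28 days from toxicity | off the responsible treatment | required |
| 8.8.2 | unresolved after 28 days | everolimus stopped; HCQ may continue | not stated; 7.8 applies |
| Table 11 | interruption > 28 days | everolimus discontinued | not stated; 7.8 applies |

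Section 8.7 (major events) and Table 6 (hepatitis B) also stop only treatment or study drug when a problem outlasts 28 days. Section 8.4 and Table 4 are therefore the exceptions.

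**2. Can the two be reconciled?** Section 7.7 allows removal before full follow-up for unacceptable toxicity, and 7.8 lets the investigator end a subject's "participation for any reason, including adverse event or failure to comply with the protocol". Both are discretionary. They do not turn the mandatory wording of 8.4 and Table 4 into a case-by-case choice. The HCQ-alone option in 8.4 does not cover every patient either: under Section 7.1, Arm B receives only everolimus in cycles 1 to 6, so those patients have no HCQ to continue.

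**3. What a literal reading ends.** Section 5.4 schedules one visit 30 days after the last dose and then 6-monthly visits for 3 years.

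Visits = 1 + (3 years × 2 per year) = 7.

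The disease check 6 months after the last dose (Section 5.6) would also be lost.

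**4. Who could be affected.** At 15 per arm (Section 1), Arms B, C and D plan everolimus in the first six treatment cycles: 3 × 15 = 45 of 60. Redirecting Arm C allocations to Arm D under Amendment 7 does not change that total. Patients from Arm A who cross over add exposure in cycles 7 to 12. This counts patients exposed, not patients removed.

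**5. Illustration for RFS.** The documents give no rate for everolimus delays over 28 days or for unresolved pneumonitis. Let k be the number of enrolled patients whose 3-year status is unknown for this reason. The gap between the best and worst case for 3-year RFS is k/n. Section 12.2.2 plans the estimate for enrolled patients, so n = 60:

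- k = 1: 1/60 = 1.7 percentage points
- k = 2: 2/60 = 3.3
- k = 3: 3/60 = 5.0

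These values of k are assumptions.

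**6. Primary endpoint.** A patient taken off treatment before the end of cycle 6 has not completed six cycles under either reading. A patient removed in cycles 7 to 12 has already passed the feasibility time point. The endpoint is therefore largely unaffected.

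**The case against.** The best defence is that the intended meaning can be recovered. Section 7.8 is the dedicated discontinuation section, names this trigger and requires follow-up. Section 7.9 treats withdrawal that includes follow-up as the patient's own written request. Most sites would probably read 8.4 and Table 4 as stopping treatment. That is fair, and it limits the expected harm. It does not make the instructions agree, and it is itself a reason to correct the words.

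Four further objections stand, and each limits what can be claimed.

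- **Safety follow-up.** A reader might infer that removed patients lose toxicity monitoring. The documents do not support this. Section 8.4 itself says patients stopped for everolimus toxicity "must be followed at least weekly until the adverse event or abnormal laboratory resolves or returns to grade" 1 or less, and Sections 5.4 and 10.2 separately require unresolved adverse events to be followed.
- **HCQ.** Section 8.8.2 only permits HCQ to continue, so the conditions in 8.4 could be read as narrowing that permission rather than contradicting it. The two places still state different rules.
- **Clinical benefit.** A reader might infer that no benefit could be measured, because these patients have no tumor. Section 11.1.3 makes marrow DTCs the measurable disease. The term is undefined, which is a smaller fault.
- **RFS.** The estimate is unpowered, and Section 5.6 calls time-to-event analyses beyond the pilot's scope.

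On the cross-reference, Section 3.5.4 cites Table 4 correctly and Section 8.5.3 points to 8.6.6. A clinician who opened a hepatitis table would probably notice the mistake. No risk of wrongly given antivirals is shown.

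**Conclusion.** The inconsistency is real and should be corrected. Section 8.4 and Table 4 (grades 2 and 3) require removal from the study where 7.8, 8.8.2 and Table 11 stop a drug, and 7.8 keeps the patient in follow-up. Read literally, they end up to 7 visits and recurrence follow-up per affected patient, with the loss driven by everolimus toxicity. The consequence falls on the unpowered 3-year RFS estimate. How many patients are affected cannot be derived from the documents, and the gap of 1.7 to 5.0 points rests on an assumed one to three patients out of 60.

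Two stronger readings should not be drawn. Dividing k by an arm of 15 gives larger gaps, but Section 12.2.2 plans RFS for the enrolled patients and does not set out estimates by arm. Nor can loss of the end-of-cycle-6 marrow be blamed on 8.4: Section 5.3 ties that sample to cycle 6, so for a patient who stops all treatment early, 7.8 does not clearly guarantee it either.

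The Table 6 reference is a plain error, made twice.

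**What to change.** 1. In Section 8.4 and in Table 4 grades 2 and 3, replace removal from the study with discontinuation of everolimus (or study treatment), with follow-up per Section 7.8. The 2- and 3-week limits for pneumonitis can stay.
2. In Section 8.4, state one rule on continuing HCQ for patients already receiving both drugs, and put the same rule in Section 8.8.2. For example: HCQ may continue once toxicity is below grade 2. It should cover Arms C and D, and Arm A and B patients after crossover.
3. Delete the undefined clinical-benefit condition in both 8.4 and Table 4 grade 3, where it governs restarting treatment.
4. In Table 11, change both pneumonitis references from Table 6 to Table 4.

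The cost is a wording amendment plus continued follow-up of whichever patients meet these triggers. No dose level, sample size or endpoint changes.
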